6.2 Treatment Regimens

Unless otherwise specified, the safety and efficacy analysis will be based on the treatment group “as treated”.

6.3 Populations for Analyses

For purposes of analysis, the following populations are defined:

Population	Description
Enrolled	All participants who sign informed consent
Treated	All participants who take any dose of study treatment.
Pharmacokinetic	All treated participants who have evaluable concentration-time data
Immunogenicity	All treated participants who have baseline and at least one post baseline pre-infusion immunogenicity assessment

7 STATISTICAL ANALYSES

7.1 General Methods

Unless otherwise noted, discrete variables will be tabulated by the frequency and proportion of subjects falling into each category, grouped by treatment. Percentages given in these tables will be rounded to the first decimal and, therefore, may not always sum to 100%. Continuous variables will be summarized by cohort using the mean, standard deviation, median, minimum, and maximum values.

The conventions to be used for imputing missing and partial dates for analyses requiring dates are described in [Section 8](#).

7.1.1 Adverse Events, and Serious Adverse Events

Drug-related AEs are those events with relationship to study drug “Related”, as recorded on the CRF. If the relationship to study drug is missing, the AE will be considered as drug-related.

Serious adverse events consist of AEs deemed serious by the Investigator and flagged accordingly in the CRF and clinical database.

Adverse events leading to study drug discontinuation are AEs with action taken regarding study drug(s) = “Drug was discontinued”.

Adverse events leading to dose delay are AEs with action taken regarding study drug(s) = “Drug was delayed”.

Adverse events will be coded using the Medical Dictionary for Regulatory Activities (MedDRA), and the most recent version of the dictionary at the time of the database lock will be used. Adverse events results will be graded for severity using NCI Common Terminology Criteria for Adverse Events (CTCAE) and the most recent version of the criteria at the time of the database lock will be used.

In the AE summary tables, unless otherwise specified, subjects will be counted only once at the Preferred Term (PT), only once at the System Organ Class (SOC), and only once at subject level for the counting of total number of subjects with an AE. The AE tables will be sorted by the SOCs and then PTs. SOC will be ordered by descending frequency overall and then alphabetically. PTs will be ordered within SOC by descending frequency overall and then alphabetically. The sorting will be done based on the ‘Any Grade’ column of the experimental arm when arms are presented side-by-side.

Unless otherwise specified, the AE summary tables will be restricted to on-treatment events regardless of the causality.

7.1.1.1 Other Events of Interest

Other events of interest (OEOI) consist of a list of preferred terms grouped by specific category (e.g. Periorbital Edema, AST Abnormality, ALT Abnormality, CK Abnormality, Myositis Event, Myocarditis Event, Demyelination Event, Guillain-Barre Syndrome, Pancreatitis Event, Uveitis Event, Encephalitis Event, Myasthenic Syndrome, Rhabdomyolysis Event, Graft Versus Host Disease). The list of MedDRA preferred terms used to identify OEOI is revisited quarterly and updated accordingly. The preferred terms used for the selection at the time of the database lock by categories will be provided.

7.1.2 Laboratory Tests

Clinical laboratory parameters (hematology, serum chemistry and electrolytes) will be evaluated.

Laboratory tests will be graded using the NCI Common Terminology Criteria, and the most recent version of the criteria at the time of the database lock will be used.

Clinical laboratory data will be analyzed using International System of Units (SI).

In the laboratory summary tables, unless otherwise specified, subjects will be counted only once for each lab parameter according to their worst on treatment CTC grade (worst being the highest CTC grade). The laboratory tables and listings will be sorted by laboratory category, laboratory subcategory and laboratory test code sequence number.

7.1.3 *Immunogenicity Data*

Blood samples for immunogenicity analysis will be collected from subjects according to the protocol schedule. Samples will be evaluated for development of Anti-Drug Antibody (ADA).

7.2 *Study Conduct*

Enrollment by country and site will be summarized and listed for all enrolled subjects.

A by-subject listing of batch numbers for all treated subjects will be provided.

7.3 *Study Population*

Analyses in this section will be tabulated for all enrolled subjects by cohort, unless otherwise specified.

7.3.1 *Subject Disposition*

The total number of subjects enrolled (treated or not treated) will be presented along with the reason for not being treated. This analysis will be performed on the all enrolled subjects population only.

Number of subjects who discontinued study treatment along with corresponding reason will be tabulated by cohort. Reason for discontinuation will be derived from subject status CRF page. This analysis will be performed only on the all treated subjects population.

A by-subject listing for all treated subjects will be provided showing the subject's off treatment date and whether the subject continue in the treatment period/study along with the reason for going off treatment period/study. A by-subject listing for all enrolled subjects will also be provided, showing whether the subject was treated along with the reason for not being treated.

7.3.2 *Demographics and Other Baseline Disease Characteristics*

The following demographic and baseline characteristics will be summarized and/or listed by cohort:

Solid Tumor (Cohort M1, M2, and C1)

Summary:

The following subject demographics and baseline characteristics will be summarized for all treated subjects by cohort.

- Age (in years) ; age category (<65, \geq 65)

- Gender
- Race
- ECOG PS
- Prior therapy (surgery, radiotherapy, systemic cancer therapy)

Listing:

- All relevant data, generally variables listed above by cohort.
- Listing of Baseline disease characteristics
- Listing of Gene Mutation Status

MM (Cohort C2)

Summary:

The following subject demographics and baseline characteristics will be summarized for all treated subjects by cohort.

- Age (in years) ; age category (<65, \geq 65)
- Gender
- Race
- ECOG PS
- Prior therapy (surgery, radiotherapy, systemic cancer therapy)
- Serum M-protein (g/dL)
- Urine M-protein (mg/24 hours)
- Number of lytic bone lesions (0, 1-3, >3)
- Soft tissue plasmacytomas (Yes, No)
- Myeloma type (IgG, IgA, IgM, Light chain disease)
- ISS Stage (I, II, III)

Listing:

- All relevant data, generally variables listed above by cohort.
- Albumin (g/L) (<3.5, \geq 3.5)
- LDH (<300 IU/L, \geq 300 IU/L)
- Individual FISH/Cytogenetic abnormalities (del 17p, t(14; 16), t(4; 14))

7.3.3 *Medical History*

A by-subject listing of general medical history for all treated subjects will be provided.

7.3.4 Prior Therapy Agents

Prior therapy will be summarized by cohort and overall.

7.3.5 Physical Examinations

Subjects with baseline physical examination will be listed by subject.

7.3.6 Baseline Physical Measurements

Baseline physical measurements will be listed by subject.

7.4 Extent of Exposure

Listings will include all available exposure data. Analyses will be performed by cohort “as treated” in all treated subjects, unless otherwise specified.

7.4.1 Administration of Study Therapy

The following parameters will be summarized (descriptive statistics) by study therapy and cohort:

- Number of doses received
- Cumulative dose
- Relative dose intensity (%) using the following categories: < 50%; 50 - < 70%; 70 - < 90%; 90 - < 110%; ≥ 110%

Duration of study therapy will be summarized (descriptive statistics) by cohort.

A by-subject listing of dosing of study medication (record of study medication and dose changes) will be also provided.

Table 7.4.1-1: Administration of Study Therapy - Definition of Parameters

BMS- 986227 and Nivolumab	
Dosing schedule per protocol	BMS- 986227: 2 mg/kg or 4 mg/kg every 2 weeks Nivolumab: 3 mg/kg every 2 weeks (Cohort C1, C2 only)
Dose	Dose (mg/kg) is defined as Total Dose administered (mg)/Most recent weight (kg). Dose administered in mg at each dosing date and weight are collected on the CRF.
Cumulative Dose	Cum dose (mg/kg) is sum of the doses (mg/kg) administered to a subject during the treatment period.
Relative dose intensity (%)	BMS- 986227: $[(\text{Cum dose (mg/kg)} / ((\text{Last dose date} - \text{Start dose date} + 14) \times 14)) \times 100]$ Nivolumab: $[(\text{Cum dose (mg/kg)} / ((\text{Last dose date} - \text{Start dose date} + 14) \times 14)) \times 100]$

Table 7.4.1-1: Administration of Study Therapy - Definition of Parameters

BMS- 986227 and Nivolumab	
Duration of study therapy	(Last dose date of any study drug - Start dose date of any study drug +14)/7, where the last dose date is event date for subjects who discontinued study therapy. Subjects who are still on therapy will be censored on their last dose date.

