7.5.1 Dosing of Cabiralizumab and Nivolumab

For patients in the monotherapy cohorts, cabiralizumab infusion will be administered as a 30-minute IV infusion on Day 1 of each 14-day treatment cycle. For the combination therapy, nivolumab should always be administered first as a 30-minute IV infusion followed by a 30-minute infusion of cabiralizumab. The time in between infusions is expected to be approximately 30 minutes but may be more or less depending on the situation. Cabiralizumab ± Nivolumab will be administered every 2 weeks in 14-day (\pm 2 days). Subjects may be dosed no less than 12 days from the previous dose.

Dosing calculations should be based on the body weight assessed at Cycle 1 Day 1 prior to the first dose of study drug administration. If the subject's weight on the day of dosing differs by $> 10\%$ from the weight used to calculate the prior dose, the dose must be recalculated. All doses should be rounded to the nearest milligram.

The calculated dose for Cabiralizumab may be mixed in 5% Dextrose Injection, USP or 0.9% Sodium Chloride Injection, USP to nominal concentrations of 1.0 mg/mL to 10 mg/mL which can be infused over a period of 30 minutes through an intravenous line containing a sterile 0.22 micron in-line filter. Further guidance and information for the preparation of the study medication is provided in the pharmacy manual.

The calculated dose for Nivolumab may be mixed in 5% Dextrose Injection, USP or 0.9% Sodium Chloride Injection, USP to nominal concentrations of 1 mg/mL – 10 mg/mL which can be infused over a period of 30 minutes through an intravenous line containing a sterile, non-pyrogenic, low-protein binding in-line filter. Further guidance and information for the preparation of the study medication is provided in the pharmacy manual.

[figure not shown]
Doses of study drugs may be interrupted, delayed, or discontinued depending on how the patient tolerates the treatment.

[figure not shown]
[figure not shown]
[figure not shown]
7.5.2 *Retained Samples for Bioavailability / Bioequivalence*

Not Applicable.

7.6 *Treatment Compliance*

Study treatment compliance will be periodically monitored by drug accountability. Drug accountability should be reviewed by the site study staff at each visit to confirm treatment compliance. Sites should discuss discrepancies with the participant at each on-treatment study visit.

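### SAP 7.4.1: the relative dose intensity formula omits the planned dose and multiplies by 14 where it should divide, so on-schedule dosing scores 1.02–2.04% instead of 100%

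*SAP*

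**What the plan says.** SAP 7.4.1 summarises exposure by number of doses, cumulative dose, RDI and duration. It introduces "Relative dose intensity (%) using the following categories": below 50%, 50 to below 70%, 70 to below 90%, 90 to below 110%, and 110% or more.

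Table 7.4.1-1 gives the definitions:

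- **Planned schedule:** "BMS- 986227: 2 mg/kg or 4 mg/kg every 2 weeks" for cabiralizumab, and 3 mg/kg every 2 weeks for nivolumab in C1 and C2.
- **Cumulative dose:** it "is sum of the doses (mg/kg) administered to a subject during the treatment period".
- **RDI, same line for each drug:** cumulative dose divided by the product of (last dose date − start dose date + 14) and 14, then times 100. The expression closes with "Start dose date} + 14) \times 14)) \times 100". The brackets balance and put the factor 14 inside the denominator.
- **Duration:** the same kind of date difference plus 14, divided by 7 to give weeks.

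No other section of the SAP or protocol defines RDI differently.

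**The concern.** RDI should compare drug received with drug planned over the same time. This formula contains no planned dose, so it is relative to nothing, although the planned doses stand in the first row of the same table. The second problem is the 14. Days on treatment divided by 14 give the number of planned cycles; days multiplied by 14 give nothing meaningful. The result has units of mg/kg per day (per day squared if the 14 is itself in days) and cannot be a percentage.

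The SAP's own categories run from below 50% to 110% or more, which makes sense only if on-schedule dosing scores about 100%. If the formula is programmed as written, the table reports severe under-dosing in all four cohorts. If a programmer silently repairs it, the reported quantity no longer matches its SAP definition. Of the summaries in 7.4.1, RDI is the only one that sets drug received against drug planned.

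**Working it through.** The plan states no numerical RDI to reproduce, so the check evaluates the formula directly.

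**Inputs.** Planned doses d = 2 or 4 mg/kg (cabiralizumab) and 3 mg/kg (nivolumab), every 14 days: SAP Table 7.4.1-1. Shortest interval: Protocol 7.5.1 says "Subjects may be dosed no less than 12 days from the previous dose".

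**Set-up.** For k doses of d mg/kg at interval i days:

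- cumulative dose = d·k
- N = last − start + 14 = i(k − 1) + 14 days
- as written: RDI = 100·d·k/(14N)
- intended: RDI = 100·d·k/(d·N/14)

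**Exactly on schedule (i = 14).** N = 14k, so the formula as written gives 100·d·k/(14·14k) = 100d/196, independent of k.

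| Dose | As written | Intended | Too small by a factor of |
|---|---|---|---|
| 2 mg/kg | 2/196 = 1.02% | 100% | 98 |
| 3 mg/kg | 3/196 = 1.53% | 100% | 65.3 |
| 4 mg/kg | 4/196 = 2.04% | 100% | 49 |

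**Off schedule, 4 mg/kg.**

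- 12-day interval, 10 doses: N = 12·9 + 14 = 122. As written 40/(122·14) = 2.34%; intended 40/(4·122/14) = 114.8%. As k grows, the written value approaches 4/(12·14) = 2.38% and never exceeds it.
- 6 doses with one 14-day delay: N = 98. As written 24/(98·14) = 1.75%; intended 24/(4·98/14) = 85.7%.
- 28-day interval, 5 doses: N = 28·4 + 14 = 126. As written 20/(126·14) = 1.13%; intended 20/(4·126/14) = 55.6%.

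The last case also shows misordering: this subject, given little over half the planned drug, scores above a fully compliant 2 mg/kg subject (1.02%).

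**What would reach 50% as written?** 0.50 × 196 = 98 mg/kg per 14 days, which is 24.5, 32.7 or 49 times the planned 4, 3 or 2 mg/kg.

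**Does a partial repair or another reading rescue it?** On schedule:

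- ×14 moved outside the denominator: 100d = 200%, 300%, 400%
- ×14 changed to ÷14, still no planned dose: 200%, 300%, 400%
- planned dose added, ×14 kept: 100/196 = 0.51% at every dose
- both changes: 100% at 2, 3 and 4 mg/kg for every k

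**The case against.** The arithmetic is hard to dispute, so the case on the other side is about provenance, weight and the remedy.

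- **A reading error.** The formula comes from a PDF table cell read by a program. If a short term such as a planned dose over 14 lost its numerator, that one loss would produce both faults at once, and it could recur in both drug lines. Balanced brackets and matching lines do not rule this out. There is, however, no gap or redaction mark in the cell, and the accumulation index and effective half-life formulas in SAP 7.7.4 came through coherently. An artefact is possible but unproven, so the advice to check the printed page stands.
- **One slip, not two.** A single missing planned-dose-over may well be the cause. That changes the account of how it happened, not the result.
- **Little practical harm.** RDI feeds no endpoint or decision, scores of 1–2% would be conspicuous in output review, and number of doses, cumulative dose, duration, a by-subject dosing listing and dose delays (SAP 7.4.2.1) are reported anyway. This is right and limits the severity. It does not make the stated definition usable.
- **The remedy needs a definition.** SAP 2.2 allows a lower dose than M1, alternative dose levels in combination expansion, and treatment at a lower dose when a level exceeds the MTD. The cohort's nominal dose does not by itself settle the reference dose for those subjects. This stands and is taken up in the fix.

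**Conclusion.** The concern holds. As written, on-schedule dosing gives 1.02%, 1.53% or 2.04% instead of 100%, and at the planned doses no schedule the protocol allows takes a subject above 2.38%. The five-category table would therefore put everyone below 50% and carry no information, and M1 and M2 could not be compared because the score scales with the assigned dose.

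The consequence is limited to one descriptive exposure summary. The conclusion assumes that the printed SAP page matches the text available here; if the page shows the planned dose over 14, the point falls away. It should be corrected before the exposure tables are produced.

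**What to change.** First compare the two RDI lines in Table 7.4.1-1 with the printed page. If they read as above, replace both with:

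RDI (%) = cumulative dose (mg/kg) ÷ [planned dose (mg/kg) × (last dose date − start dose date + 14)/14] × 100

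Keep the table's existing definition of dose in mg/kg. Add one sentence stating that the planned dose is the assigned dose for that drug and cohort, and which planned dose serves as reference for any subject covered by the dose options in SAP 2.2. This is an analysis definition only and says nothing about which dose should be given.

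The cost is two table lines and a sentence. The planned doses are already in Table 7.4.1-1 and Table 2.2-1, and neither data collection nor trial conduct changes.

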7.4.2 Modifications of Study Therapy

7.4.2.1 Dose Delays

Each nivolumab and BMS-986227 infusion may be delayed. A dose will be considered as actually delayed if the delay is exceeding 3 days (i.e. greater than or equal to 4 days from scheduled dosing date) for nivolumab and BMS-986227. All study drugs must be delayed until treatment can resume. Reason for dose delay will be retrieved from CRF dosing pages.

The following parameters will be summarized by cohort:

- Number of subjects with at least one dose delayed, the number of dose delays per subject, the reason for dose delay and the length of dose delay.

7.4.2.2 Infusion Interruptions and Rate Changes

Each nivolumab or BMS-986227 infusion can be interrupted and/or the IV infusion rate can be reduced. This information will be retrieved from CRF dosing pages.

The following parameters will be summarized by cohort:

- Number of subjects with at least one dose infusion interruption, the reason for interruption, and the number of infusion interruptions per subject.
- Number of subjects with at least one IV infusion rate reduction, the reason for reduction and the number of infusion with IV rate reduction per subject.

7.4.2.3 Dose Escalations

Dose escalations (within subject) are not permitted for either nivolumab or BMS-986227.

7.4.3 Dose Reductions

Dose reductions (within subject) are not permitted for either nivolumab or BMS-986227.

7.5 Efficacy

The efficacy analyses will be performed based on all treated subjects unless otherwise specified. The following will be listed by cohort.

Solid Tumor (cohort M1, M2, C1)

- Tumor lesion measurements
- Tumor evaluation at each visit
- Subject level efficacy - best overall response (BOR) and Duration of response (DOR) for responders

MM (cohort C2)

- Percent change in serum and urine M-protein, from baseline and nadir.
- Corrected Calcium results
-
- Serum and urine immunofixation test results
- Subject level efficacy - best overall response (BOR) and Duration of response (DOR) for responders

7.6 Safety

Analyses in this section will be tabulated for all treated subjects by cohort, unless otherwise specified.

7.6.1 Deaths

Deaths will be summarized by cohort:

- All deaths, reasons for death.
- Deaths within 30 days of last dose received, reasons for death.

A by-subject listing of deaths will be provided for the all enrolled subjects population.

7.6.2 *Serious Adverse Events*

Serious adverse events will be summarized by cohort:

- Overall summary of SAEs by worst CTC grade (any grade, grade 3-4, grade 5) presented by SOC/PT.
- Overall summary of drug-related SAEs by worst CTC grade (any grade, grade 3-4, grade 5) presented by SOC/PT.

All analyses will be conducted using the 30-day safety window.

A by-subject SAE listing will be provided for the “enrolled subjects” population.

7.6.3 *Adverse Events Leading to Discontinuation of Study Therapy*

AEs leading to discontinuation will be summarized by cohort:

- Overall summary of AEs leading to discontinuation by worst CTC grade (any grade, grade 3-4, grade 5) presented by SOC/PT.
- Overall summary of drug-related AEs leading to discontinuation by worst CTC grade (any grade, grade 3-4, grade 5) presented by SOC/PT.

The analyses will be conducted using the 30-day safety window.

A by-subject AEs leading to discontinuation listing will be provided.

7.6.4 *Adverse Events*

Adverse events will be summarized by cohort.

The following analyses will be conducted using the 30 days safety window only:

- Overall summary of any AEs by worst CTC grade (1, 2, 3, 4, 5, not reported, total) presented by SOC/PT.
- Overall summary of any non-serious AEs presented by SOC/PT.
- Overall summary of drug-related AEs by worst CTC grade (1, 2, 3, 4, 5, not reported, total) presented by SOC/PT.

The following analyses will be conducted using the 30 days safety window and repeated using the 100 days safety window:

- Overall summary of drug-related AEs by worst CTC grade (any grade, grade 3-4, grade 5) presented by SOC/PT.

A by-subject AE Listing will be provided.

7.6.5 *Other Events of Interest*

OEOI will be summarized by cohort for each category.

The following analyses will be conducted using the 100-day safety window:

- Overall summary of OEOI by worst CTC grade (any grade, grade 3-4, grade 5) presented by Category / PT
- Overall summary of drug-related OEOI by worst CTC grade (any grade, grade 3-4, grade 5) presented by Category / PT

A by-subject listing of OEOI will be provided.

7.6.6 *Laboratory Parameters*

The analysis population for each laboratory test is restricted to treated subjects who underwent that laboratory test. Laboratory tests (in addition to the tests specified below) with CTC criteria collected in the specific studies may also be included in the summaries.

7.6.6.1 *Hematology*

The following will be summarized by cohort as worst CTC grade on-treatment per subject and as shift table of worst on-treatment CTC grade compared to baseline CTC grade per subject: hemoglobin (HB), platelets, white blood counts (WBC), absolute neutrophils count (ANC) and lymphocyte count (LYMPH).

The analyses will be conducted using the 30-day safety window.

A by-subject listing of these laboratory parameters will be provided.

7.6.6.2 *Serum Chemistry*

The following will be summarized by cohort as worst CTC grade on-treatment per subject and as shift table of worst on-treatment CTC grade compared to baseline CTC grade per subject: ALT, AST, alkaline phosphatase (ALP), total bilirubin and creatinine.

The analyses will be conducted using the 30-day safety window.

A by-subject listing of these laboratory parameters will be provided.

7.6.6.3 *Electrolytes*

The following will be summarized by cohort as worst CTC grade on-treatment per subject and as shift table of worst on-treatment CTC grade compared to baseline CTC grade per subject: sodium (high and low), potassium (high and low), calcium (high and low), magnesium (high and low), and Glucose Serum (fasting hyperglycemia and hypoglycemia regardless of fasting status)

The analyses will be conducted using the 30-day safety window.

A by-subject listing of these laboratory parameters will be provided.

7.6.6.4 *Abnormal Hepatic Test*

Summary:

The number (%) of subjects with the following laboratory abnormalities from on-treatment evaluations will be summarized by treatment group, provided at least 5 subjects with an abnormality within at least one treatment group. Otherwise, only listing and plot will be provided:

- ALT or AST > 3 x ULN, > 5 x ULN, > 10 x ULN, > 12 x ULN and > 20 x ULN
- Isolated Total bilirubin > 2 to \leq 3 x ULN
- ALT or AST > 20 x ULN or Total bilirubin > 3 x ULN
- Concurrent (within 3 days) ALT or AST > 3 x ULN and Total bilirubin > 2 x ULN
- Concurrent (within 3 days) ALT or AST > 5 to \leq 12 x ULN and Total bilirubin \leq 2 x ULN
- Concurrent (within 3 days) ALT or AST > 12 to \leq 20 x ULN and Total bilirubin \leq 2 x ULN

Figure:

- Scatter plot of Total bilirubin peak vs AST peak
- Scatter plot of Total bilirubin peak vs ALT peak

On-treatment peak total bilirubin and on-treatment peak AST/ALT may or may not happen on the same day of liver testing.

Listing:

AST or ALT elevations, combined with a bilirubin elevation (concurrent or not) will be listed.

7.6.7 *Vital Signs and Pulse Oximetry*

Vital signs and pulse oximetry (i.e. % oxygen saturation) collected on the CRF will be provided in separate listings.

7.6.8 *Physical Measurements*

Physical measurements will be listed by subject.

7.6.9 *Immunogenicity Analysis*

Incidence of ADA

Number (%) of subjects will be reported for the following parameters based on Evaluable Subjects.

- Baseline ADA-positive
- ADA-positive
 - Persistent Positive (PP)
 - Not PP-Last Sample Positive
 - Other positive

- Neutralizing Positive
- ADA-negative

A listing of all ADA assessments will be provided.

7.6.10 *Pregnancy*

A by-subject listing of pregnancy tests results will be provided for enrolled female subjects.

7.7 *Pharmacokinetics*

All available serum concentration-time data from subjects who receive BMS-986227 and/or Nivolumab will be reported. All available derived PK parameter values of BMS-986227 will be included in the PK dataset and reported, but only subjects with adequate PK profiles will be included in summary statistics and statistical analysis.

7.7.1 *Contraction-Time Data*

Participant concentration-time profiles will be listed and summarized by cohort and nominal collection time for BMS-986227 and Nivolumab. Overlay of individual concentration profiles over time will be provided by cohort. Plots of mean (+SD) concentration profiles versus time will be presented by cohort on the same plot.

7.7.2 *PK Parameters*

Summary statistics will be tabulated for each PK parameters by cohort for BMS-986227. Geometric means and coefficients of variation will be presented for Cmax, AUC(0-t), AUC(TAU), AI_Ctrough, T-HALFeff_Ctrough. Medians and ranges will be presented for Tmax. All individual PK parameters will be listed including any exclusions.

7.7.3 *Ctrough*

Ctrough values will be listed and summarized by cohort and time point. To evaluate the steady state of BMS-986227 and Nivolumab concentration in the body, the geometric means of Ctrough vs. cycle will be plotted by cohort with individual participant measurements superimposed in the plots.

7.7.4 *Accumulation and Effective Half-life*

To assess drug accumulation over the course of dosing in this study, drug accumulation indices

$$AI = \frac{C_{trough \text{ on Cycle 8}}}{C_{trough \text{ on Cycle 2}}}$$

where $k > 1$ is each subsequent study day with serial PK sampling, and, if $AI > 1$,
effective half-lives

$$\text{Effective half-life} = \frac{\text{Dose Interval} \times \log(2)}{\log(AI/(AI-1))}$$

will be computed for each subject and day of serial PK sampling after Day 1. If it is clear that the drug does not accumulate ($AI \leq 1$), then omit effective half-lives. These values will be included in the appendix listing of PK parameters and the supplemental table of summary statistics.

